## G. Detailed study procedures: recruitment and retention

Personnel from three organizations will have contact with study participants or their data. Staff at Optum, operator of the WTQL, will recruit, screen, consent, assess, randomize, and deliver treatment to participants. Personnel from ICF International, the operator of SmokefreeTXT, will not have direct contact with participants, since SmokefreeTXT is a fully automated texting program. Personnel at ICF International will, however, transmit participant data on use of SmokefreeTXT, cell phone numbers, and basic demographics. Finally, UW-CTRI personnel will interact with participants to conduct follow-up telephone interviews (12- and 26-weeks post-quit

day) and to collect biochemical saliva samples via mail, collect breath carbon monoxide (CO) test results via email, or biochemically verify abstinence at brief in-person visits at UW-CTRI offices (26-weeks post-quit day) among some or all of the participants who claim they have not smoked in the last 7 days at the 26-week follow-up interview. The table below details the activities that participants will complete during the study and identifies the entity responsible for implementation. Coordination of all activities will be led by UW-CTRI and UW-CTRI will perform all data analyses.

As shown below, recruitment will be conducted by designated staff at the WTQL by inviting the subset of registered quit line callers meeting study eligibility prerequisites to screen for a study evaluating program enhancements for smokers who want to quit within 2 weeks. Staff at UW-CTRI will communicate with the WTQL team working on this project at least monthly to monitor progress in recruitment, treatment engagement (i.e., retention), and implementation challenges. To promote recruitment, WTQL staff will make at least 5 attempts to reach prospective enrollees. Similarly, to promote retention, WTQL Quit Coaches will make at least 5 attempts to schedule/deliver each counseling session by telephone. Letters will be sent to individuals meeting study prerequisites to encourage them to reconnect with the WTQL. Staff at the WTQL will be responsible for processing incentive payments to participants as soon as possible after they are earned. Staff at the WTQL will also be responsible for assessing adverse events related to its interventions in accordance with their existing protocols (i.e., staff physician review).

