4. Follow-up assessment (see uploaded follow-up assessment). At 12- and 26-weeks following the target quit day, participants will be asked to report on recent use of tobacco and smoking cessation products and associated costs, treatment satisfaction, and levels of candidate mediators of intervention effects (nicotine withdrawal distress, confidence, motivation, exposure to smoking triggers, and perceptions of stress, support, or control). Participants will earn \$30 for completing each of these calls. At the 12-week call, participants will also be asked whether the research team may email them reminders about the final follow-up at 26 weeks.

At 26 weeks following the target quit day, individuals claim to have not had even a puff of a cigarette in the past 7 days may be asked to schedule a verification visit at which they will be asked to provide a breath sample for carbon monoxide (CO) testing using the commercially available Micro+Smokerlyzer® from Bedfont Scientific Ltd. and a urine sample for cotinine testing to confirm abstinence. These biochemical verification procedures present minimal risk, as they require only that participants hold their breath for 15 seconds before blowing into a CO detector and that participants urinate in a cup. In order to achieve a high level of abstinence verification, and in light of participant travel involved, participants will receive \$40 for completing this visit. Participants may be asked to complete alternative testing to verify abstinence remotely. This may entail mailing back a saliva sample for cotinine testing or emailing the research team a CO test using a personal CO monitor, and will similarly earn participants \$40.

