We have defined the window for the follow-up periods broadly (11-18 weeks for the follow-up targeted to 12 weeks post-quit and 25-38 weeks for the follow-up targeted to 26 weeks post-quit) in order to maximize retention in a participant population that may experience socioeconomic conditions that impede connection (e.g., phone disconnections, relocation). We seek to maximize follow-up ascertainment by keeping the follow-up windows broad and making many attempts to contact participants within these windows. We will leave discreet voicemails (identifying the study by its nickname, the IQS Study, without revealing the nature or purpose of the study) to participants who consented to voicemails at the time of enrollment in quitline services. Data analysis strategies will take into account the breadth of the follow-up windows and will use late follow-up data (e.g., those more than 2 weeks from the target follow-up date) to inform sensitivity analyses to assess the robustness of results under varying inclusion criteria for these cases and assumptions about missingness in a tighter follow-up window. We will cease attempts to complete a follow-up if a participant declines the interview, complains about our calling, or reaches the end of the follow-up window without being reached.

	Schedule of Study Activities	Imple- menter
Standard WTQL Treatment	
 
• Registration (tobacco history, demographics, insurance, education, chronic health conditions, county,)
 
• 1 proactive counseling call
 
• 2-week NRT monotherapy starter kit
 
• Unlimited coaching calls (initiated by smoker)
 
 
Anticipated N=7,963
	WTQL
~4-Month Follow-Up	
 
• Assess smoking status (past 7 days)
 
 
Anticipated # Reached N=3,185
	WTQL
Eligibility Screening (Attach- ment A)	
 
• Screen relapsers for inclusion/exclusion criteria
 
• Set quit date within 2 weeks
 
 
Anticipated # Eligible N=2,548
	WTQL
Oral Consent (uploaded)	
 
• Describe study
 
• Elicit and answer questions
 
• Obtain & document consent
 
 
Anticipated # Enrolled N=1,408-1,600
	WTQL

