26-Week Follow Up (Attach- ment G)	
 
• Self-reported tobacco use & costs in past 7 days & since target quit date 
 
- Those claiming abstinence in last 7 days may be invited for CO and/or cotinine testing at a research office, or via mailed saliva collection kit or personal CO monitor for verification of abstinence, and will be paid \$40 payment for test completion.
 
 
 
• Treatment use, adherence, satisfaction, & costs
 
• Mediators (reduction in exposure to smoking/triggers; motivation & confidence)
 
	UW- CTRI

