## Analysis Plan

To assess Aim 1, we will test the main and interactive effects of counseling intensity, NRT intensity, SmokefreeTXT, and engagement incentives on biochemically confirmed, 7-day point-prevalence abstinence at 6-month follow-up. Secondary abstinence outcomes are self-reported point-prevalence abstinence 12-weeks post-quit and continuous abstinence between months 1 and 6 post-quit.

*Measures, Populations and Analysis:*

Data for the primary, abstinence-focused analyses will include randomized levels of the treatment factors and their interactions as independent variables, binary abstinence outcomes based on self-reported abstinence (at 12-week follow-up) and biochemical verified abstinence (at 26-week follow-up only) as the dependent variables, and covariates such as demographics and smoking history collected at registration or enrollment.

The population will be the eligible, consented, enrolled subjects who were randomized to treatment. Participants who were randomized but did not complete the study will be included in analyses (unless they requested that their data not be used upon withdrawal from the study). Analyses will occur in the full intent-to-treat sample.

Logistic regression analyses will be used to estimate intervention main and interactive effects on binary abstinence outcomes. Both unadjusted models and models adjusted for covariates will be run. Separate models will be run for different outcomes (e.g., biochemically confirmed abstinence at 26-weeks post-quit, self-reported abstinence at 12 weeks post-quit, continuous abstinence between 4 and 26-weeks post-quit) under different assumptions regarding missing abstinence data (e.g., assuming all missing are smoking, assuming 80% of missing are smoking, using multiple imputation).

*Data Sources and Collection:* The primary outcome data will be collected by UW-CTRI via telephone follow-up interview and in-person, mailed, or emailed validation of abstinence via CO breath testing and/or urinary or salivary cotinine testing. Covariates will be assessed by WTQL staffers at registration or enrollment and transferred securely to UW-CTRI for analysis.

To assess Aim 2, we will evaluate the costs and cost-effectiveness of each intervention component overall and in the context of the other components (i.e., additive and interactive effects and their impact on cost-effectiveness).

*Measures, Populations and Analysis:*

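### A declined interview closes the follow-up with no fallback question on 7-day smoking, so reached participants go avoidably missing; the resulting bias under missing-equals-smoking is small unless declines differ widely by factor level

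*Combined protocol and SAP*

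**What the plan says.** The rule stands with the follow-up windows in the Assessment Plan (item 4, Follow-up assessment): "We will cease attempts to complete a follow-up if a participant declines the interview, complains about our calling". The third trigger is the end of the window. No section describes a shortened interview, a minimum data set or a single smoking-status item for someone who declines.

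The interview covers "recent use of tobacco and smoking cessation products and associated costs, treatment satisfaction, and levels of candidate mediators of intervention effects", and the Schedule of Study Activities adds treatment use and adherence. The form is an uploaded attachment that is not in the reviewed file, and no duration is stated.

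The primary outcome is "biochemically confirmed, 7-day point-prevalence abstinence at 6-month follow-up". It therefore takes a self-report followed by a test, and the plan leaves the extent of testing open: "some or all of the participants who claim they have not smoked in the last 7 days". The 12-week outcome is self-report only.

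The Analysis Plan gives three examples for missing abstinence data: "assuming all missing are smoking", treating 80% of the missing as smokers, and multiple imputation. None is named as primary. Analyses are in the full intent-to-treat sample.

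**The concern.** A participant who is on the telephone and declines has already been reached, which the same paragraph presents as the hard step in this population. That paragraph also sets out to get as many follow-ups as possible and widens the 26-week window to 25-38 weeks for the purpose. Closing the contact without asking the one item on which every abstinence outcome begins works against that aim.

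Two things are at stake. Some missing smoking-status data are avoidable. And if declines are more frequent at one level of a factor than the other, counting decliners as smokers shifts that factor's contrast. The Consent section itself recognises possible attrition in conditions with little or no incentive money. Blinding the follow-up staff does not stop participants' own willingness to be interviewed from differing by condition.

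**Working it through.** **Inputs from the documents.** The target is 1,408-1,600 randomized (section A). Each factor splits the 16 cells in half, giving n = 1,408/2 = 704 to 1,600/2 = 800 per level. The plan states no significance level, power, base abstinence rate, effect size, dropout or decline rate, so its sample size cannot be reproduced and everything below rests on assumed rates.

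**Notation.** p is true verified abstinence, equal at both levels (no real effect). q is verifiable abstinence among decliners. m1 and m0 are the decline rates at the two levels.

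**Step 1: bias under missing-equals-smoking.** The observed rate at a level is p − m·q, so the false difference is q × (m0 − m1). With q = p and declines of 5% versus 10%:
- p = 10%: 0.10 × 0.05 = 0.50 points
- p = 15%: 0.15 × 0.05 = 0.75 points

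With declines of 3% versus 6%, the same formula gives 0.30 and 0.45 points.

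**Step 2: scale.** The standard error of a difference is √(2p(1 − p)/n).
- p = 10%: √(0.18/704) = 1.60 points; √(0.18/800) = 1.50 points
- p = 15%: √(0.255/704) = 1.90 points; √(0.255/800) = 1.79 points

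The bias is about 0.3 to 0.4 of a standard error (0.50/1.60 = 0.31; 0.75/1.79 = 0.42). At an assumed two-sided 5% level and 80% power, with base rates of 10-20%, the detectable difference is 4.95-6.3 points for 1,408 and 4.6-5.9 points for 1,600.

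**Step 3: effect on a nominal 5% two-sided pooled z-test.**

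| p | q | Declines | Bias (points) | Rejection, N = 1,408 | Rejection, N = 1,600 |
|---|---|---|---|---|---|
| 10% | 5% | 5% vs 8% | 0.15 | 5.1% | 5.1% |
| 10% | 10% | 5% vs 10% | 0.50 | 6.2% | 6.4% |
| 15% | 15% | 5% vs 10% | 0.75 | 6.9% | 7.2% |
| 20% | 20% | 5% vs 15% | 2.0 | 16.4% | 18.0% |

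The first and last rows are the extremes of the range examined.

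**Step 4: the 80% rule.** Here 20% of the missing are counted as abstinent, so the false difference is (q − 0.20) × (m0 − m1). With q = 10% and declines of 5% versus 10% it is −0.10 × 0.05 = −0.50 points: the same size as in step 1, with the opposite sign.

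**Step 5: what one question recovers.** Let v be the share of abstinent decliners who answer and are also verified. If unverified claims count as smoking, the bias left in the confirmed outcome under missing-equals-smoking is q × (m0 − m1) × (1 − v). For the 0.50-point case this leaves 0.50 at v = 0, 0.38 at v = 25%, 0.25 at v = 50% and 0 at v = 100%.

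**The case against.** The case for leaving the rule alone has real strength.

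- Stopping after a refusal respects the participant's choice. Stopping after a complaint is a protection and is not in dispute.
- A reader might infer that the interview is long. The documents give no duration and the form is not in the file. Tobacco use comes first in each description of the interview. If the call follows that order, someone who breaks off part-way has already given smoking status, and only refusals at the outset are affected.
- A reader might infer that treatment incentives drive declines. Nothing shows this. Every condition is paid $30 per follow-up call, and the consent materials separate that payment from treatment incentives in order to limit attrition. A differential is plausible, but it is not demonstrated.
- Missing-equals-smoking is one of three listed analyses, and the Assessment Plan adds sensitivity analyses on missingness.
- People who refuse a paid call may also refuse a test, so verified recovery could be low.
- The retention threats the plan names are disconnected phones and relocation, which this rule does not touch.

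These points limit the size of the problem and how much the remedy recovers. They do not give a reason against asking one voluntary question of someone already on the line. The planned alternatives show sensitivity without removing bias: step 4 replaces one assumption with another and reverses the sign.

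**Conclusion.** The point holds as a minor, inexpensive improvement. As written, a reached participant who declines is missing on 7-day smoking status, with no fallback in the reviewed text. If declines differ by factor level and some decliners are abstinent, the missing-equals-smoking analysis is biased. The size is about 0.5-0.75 points under assumed abstinence of 10-15% and declines of 5% versus 10%. It becomes material only for large differentials, such as 5% versus 15% with 20% abstinence. All these rates are assumptions.

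Three stronger readings are not supported:

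- A reader might infer that one question would rescue the primary outcome, or that answers from half the decliners would halve the bias. A decliner who reports smoking is coded as before under missing-equals-smoking. One who reports abstinence changes the confirmed outcome only if a test is also completed. The direct gains are the 12-week self-report outcome and better information for the 80% and multiple-imputation analyses. Continuous abstinence is not supplied.
- A reader might infer that the trial's main result is biased. The bias belongs to one listed analysis, and none is designated primary.
- A reader might infer that declining at 12 weeks closes the 26-week contact. The rule can be read as applying to that time point alone.

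**What to change.** Amend the rule in the Assessment Plan as follows.

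1. At the 12- and 26-week contacts, a participant who declines the interview without complaining or withdrawing is asked once, voluntarily, whether they have smoked even a puff in the past 7 days. Refusing that question is final.
2. At 26 weeks, those reporting none are offered the verification already in the protocol, remote or in person, with its existing $40 payment.
3. Flag these answers as short-form and use them in the abstinence outcomes they can inform.
4. Record declined separately from unreached, and report both by factor level.

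The question should not be extended to a message at the end of the window. Voicemails may not disclose what the study is about, the e-mail permission sought at 12 weeks covers reminders only, and such a message would re-contact people who had refused.

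The cost is a short script, a data flag and a minor amendment; the verification procedure already exists. On the downside, a few decliners may dislike the extra question, and short-form answers carry no mediator or cost data.

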## **Data management, transmission and storage**

The WTQL will collect data in a manner consistent with its current practices, with the exception that additional fields will be assessed at the WTQL follow-up for the first round of treatment (i.e., the call at which participants will be enrolled in this evaluation study). The WTQL will also record data on incentives earned and dispensed for those in the incentive condition. The WTQL maintains a secure, HIPAA-compliant database for its operations. This database will be modified for the current project to collect the additional data needed to achieve the study aims.

SmokefreeTXT also collects data on enrollee cell phone number, basic demographics, quit day, and engagement with the program (inbound messages from enrollees) in a secure and HIPAA-compliant manner. No additional data will be collected by SmokefreeTXT for the purposes of this evaluation study. SmokefreeTXT will securely transmit data on enrollee status (not reached, declined, dropped out prior to end of the program, or completed the program) at the end of the six-week program to the WTQL so staff there can process incentives for those eligible for the \$30 incentive for completion of the SmokefreeTXT program.

Staff at UW-CTRI will receive data on participants due for follow-up from the WTQL (including names and contact information) on an ongoing basis (e.g., monthly) via secure FTP transfer. Because CTRI is the entity overseeing the WTQL contract for the State of Wisconsin and all data collected through its service to Wisconsin residents, this follows long-established, HIPAA compliant data transmission procedures.

After all participants in the study reach the end of the 26-week follow-up period:

- The WTQL will send UW-CTRI relevant registration, baseline, randomization, and treatment engagement data to UW-CTRI via secure FTP transfer. This will include data on enrollees, but also data on potentially eligible WTQL callers who did not complete the enrollment call or who did not meet eligibility screening at the enrollment call (to evaluate the representativeness of the enrolled sample). For participants who do not complete the full consenting process, UW-CTRI will obtain and keep data with no HIPAA identifiers other than an assigned WTQL ID#, which is used to verify what contract service was provided.
- ICF International will send data on SmokefreeTXT utilization at the end of the project. These data will include cell phone numbers and data regarding the volume and content of messages sent by participants to SmokefreeTXT (e.g., requests for help with cravings, negative moods, or slips; responses to SmokefreeTXT queries regarding craving, mood, and smoking) and the date of withdrawal from SmokefreeTXT (if relevant).
- At UW-CTRI, data from the WTQL and SmokefreeTXT will be linked to 12- and 26-week follow-up data. All collated study data will be stored in a HIPAA-compliant and secure manner on Department of Medicine servers with UW-CTRI-controlled password access. Staff trained in human subjects research and HIPAA compliance will link these datasets using a random subject identifier and will then de-identify the data for analyses.

Although this program will evaluate interventions delivered by the WTQL, the follow-up data collection procedures and collation of data from multiple sources/sites necessary for thorough program evaluation is the responsibility of the investigators in the study at UW-CTRI. To achieve the study aims, UW-CTRI investigators require access to identifiable patient data.

## Treatment procedures description

The WTQL offers a standard, evidence-based protocol comprising a single 20-minute counseling call (plus *ad hoc* calls as initiated by the participant) and a two-week supply of an over-the-counter nicotine replacement therapy. This will be the treatment that all study enrollees will receive in the 2.5-18 months preceding study enrollment and will be the base treatment in the second round of intervention to be evaluated in terms of reach, efficacy, and cost-effectiveness in the proposed study. Four interventions will be evaluated in a fully crossed design:

- Augmented counseling (4 proactive, scheduled telephone counseling sessions with a quit coach rather than the usual-care 1 call). The content of this counseling will follow existing, evidence-based protocols used by the WTQL in states that contract for this more intensive service.
- Augmented nicotine replacement therapy (4 weeks of nicotine patch plus nicotine mini-lozenge rather than the usual-care two-week supply of nicotine patch therapy), for those meeting WTQL NRT eligibility criteria. These FDA-approved, over-the-counter medications will be dispensed with instructions to use that follow package insert specifications (e.g., using lower, 2-mg dose mini-lozenges for individuals who do not smoke within 30 minutes of waking; dispensing lower, 14-mg dose patches to individuals who smoke fewer than 10 cigarettes per day), in accordance with current WTQL practice and documentation.
- Adjunctive SmokefreeTXT support (proactive enrollment in this 6-8-week text message-based cessation support program versus none). This national program is offered at no cost to users (apart from data/minute costs charged by cellular providers about which enrollees are advised at enrollment) and is sponsored by the National Cancer Institute. This program sends up to 5 messages per day for up to 2 weeks prior to the target quit day and 6 weeks following the target quit day (total duration may be longer if participants elect to change the target quit day). The text messages offer tips to help enrollees achieve their goal of quitting smoking and offer real-time interactive tips when participants text in responses indicating cravings, negative moods, or slips. Participants have the option to reset quit dates and have the option to unsubscribe at any time by texting STOP to the program.
- Incentives for engagement (\$30 for each counseling sessions and/or staying enrolled in SmokefreeTXT for six weeks versus none). These incentives are designed to bolster motivation to stay engaged in treatment and to offset the costs and effort of treatment engagement (in terms of cell phone minutes). Research suggests that incentives improve treatment engagement which, in turn, increases success in quitting smoking.

